## 2. Study Design

This is a non-randomized study with the intent of enrolling up to 10 participants to collect up to ten completed polysomnograms. The polysomnogram montages have specifically been altered to include the investigational channels for head pitch and roll. Head pitch and roll recorded data have been added with recorded data tagged as degrees of change from the vertical (head aligned with supine torso) as 90 degrees. Eligible participants, those meeting the inclusion criteria, will provide written informed consent. We will recruit stable, previously diagnosed POSA patients who self-report persistent apnea and who are currently on treatment by PAP.

Eligible participants will come into the Sleep Center for a screening visit. Following the screening visit, qualified participants will be asked to complete one overnight sleep study (polysomnogram) monitored by staff technologists. The sensor patch will be placed on the forehead as illustrated below and calibrated along with other calibrations that are required to complete a standard polysomnogram.

POSA will be determined as per standard collection procedures and when the threshold AHI is calculated, the research technologist shall initiate the head roll from right to left at specific degree changes to eliminate apneas and hypopneas. The changes in head roll shall be accomplished by the placement of pillow wedges to keep the head stable at the particular degree settings. The pillow wedges are selected for the predetermined angle of roll. Additionally, during these maneuvers, the torso shall be maintained in the supine position for a

specific amount of time to assess the effects of head roll independent of torso position in addition to sleeping positions that are comfortable for the participant. The data will be recorded and analyzed as such utilizing standard polysomnography body position sensors.

(Illustration of head pitch and neck roll sensor)

Following collection of overnight data, data will be scored as per standard polysomnography scoring including specific scoring of head pitch and roll in correlation with other polysomnographic data. The sleep study will be reviewed by the principle investigator to determine whether the maneuvering of head pitch and roll had normalized the AHI (See Appendix A).

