## Study Procedures:

- Subject (participant) how are eligible will be scheduled for a daytime screening session at the Sleep Center located at [name] with either the Study Coordinator or Staff Research Technologist. Following the screening visit and signed consent, qualified participants shall be asked to complete an overnight sleep study (polysomnogram).
- Following the screening visit, participant will be scheduled for an overnight sleep study and participant will arrive at scheduled time, generally between the hours of 7:00 PM and 8:30 PM.
- Research Technologist greets patient, verified individual personal information and matches the assigned Participant Clinical Data Binder (PCD) including the assigned study number.
- 4. Research Technologist shall complete the demographic section of the PCD and explain the sleep study to the participant.
- 5. Research Technologist shall attach electrodes as per Sleep Systems Research Montage and escort participant to assigned sleep room and will further explain to the participant the "process" of gathering sleep study data (i.e. calibrations, use of call button and the system that will be utilized to rotate the head as per protocol.)

- Research Technologist will attach forehead sensor to the most level surface of forehead without getting too close to the eyes with medical tape. Small foam wedges may be necessary under the sensor to adjust for calibration. Research Technologist will confirm the pitch and roll angles to be 90 degrees +/- 5 degrees.
- 7. Participant is allowed to watch Television or read until "Lights Out" as determined by the Research Technologist.
- 8. Once recording has commenced the Research Technologist shall complete the scoring forms as per protocol. Once the baseline AHI for POSA is verified (generally about 2 hours following sleep) Research Technologist shall enter the Sleep room and initiate neck roll maneuvers, utilizing wedge pillows as follows:
  - a) 30 degrees on right for 45 minutes.
  - b) 60 degrees on right for 45 minutes
  - c) 90 degree (head and neck aligned with supine torso) for 45 minutes
  - d) 120 degrees to left for 45 minutes
  - e) 150 degree to left for 45 minutes.

The goal is to normalize AHI (<5).

9. If no calculated AHI indicative of POSA (>5) is achieved the participant will be awakened at 7:00 AM and discharged from Sleep Center.

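### The protocol does not mask the scoring of sleep and respiratory events to head angle, although one disputed event can decide a borderline 45-minute segment

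*Protocol*

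**What the plan says.** Section 2 (Study Design) puts head angle into the sleep recording itself: "The polysomnogram montages have specifically been altered to include the investigational channels for head pitch and roll". After the night the record is scored by standard polysomnography rules, "including specific scoring of head pitch and roll in correlation with other polysomnographic data". The investigator's task is then set out: "The sleep study will be reviewed by the principle investigator to determine whether the maneuvering of head pitch and roll had normalized the AHI". That sentence refers to Appendix A.

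Study Procedures, step 8, describes the night: "Once recording has commenced the Research Technologist shall complete the scoring forms as per protocol". Once the baseline is verified, the same role acts on head position: "Research Technologist shall enter the Sleep room and initiate neck roll maneuvers, utilizing wedge pillows as follows". Five angles follow in fixed order (30, 60, 90, 120 and 150 degrees), 45 minutes each, and the step ends with the goal of an AHI below 5.

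The Appendix A score sheet holds measured pitch, measured roll, pillow angle and AHI in a single row. It is introduced as the information the sponsor would ideally like to have. Its example values include an AHI of 25 at a roll of 90 degrees, 17.5 at 45 or 135 degrees, and 5 at 15 or 165 degrees.

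The Data Analysis section calls for scoring to AASM standards. The glossary defines hypopnea as reduced airflow followed by desaturation, without numeric limits, and divides the AHI by total sleep time. The protocol mentions no masked, independent or second scorer.

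**The concern.** Marking a borderline airflow drop as a hypopnea, or an epoch as sleep, calls for judgement. The first changes the numerator of the AHI and the second the denominator. A scorer who knows the head angle, and knows that rotation is expected to lower the AHI, can lean toward the hypothesis without intending to.

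The design offers no protection against this. It is non-randomized, has no control arm, enrols up to 10 participants and compares angles within each person. A bias tied to angle would look the same as an effect of angle. It would also pass into the secondary aim, the algorithm linking rotation to percentage reduction in AHI, and into any larger trial powered from these results.

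**Working it through.** The protocol gives no sample-size, power or error-rate figure on this point, so there is none to reproduce. The check asks how much one event matters.

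**Inputs from the protocol.** Segment length 45 minutes and threshold AHI < 5 (Study Procedures, step 8). AHI is events divided by total sleep time (Glossary).

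**Step 1: value of one event.** Segment AHI = events × 60 / minutes asleep. With 45 minutes asleep, one event is 60/45 = 1.33/h.
- 2 events: 2 × 60/45 = 2.67/h, below 5
- 3 events: 3 × 60/45 = 4.00/h, below 5
- 4 events: 4 × 60/45 = 5.33/h, not below 5
- 5 events: 5 × 60/45 = 6.67/h, not below 5

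The result changes only between 3 and 4 events. A segment with 0 to 2 events, or with 5 or more, keeps its result if one event is added or removed.

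**Step 2: less sleep.** Forty-five minutes is the largest possible denominator. With 36 minutes asleep, 3 events give 3 × 60/36 = 5.00/h, which is not below 5, so the change falls between 2 and 3 events. With 30 minutes asleep one event is worth 2.0/h, and the change again falls between 2 and 3.

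**Step 3: how often a segment sits at the boundary.** The documents give neither an event distribution nor a true AHI by angle. Assume Poisson counts with mean m = true AHI × 0.75 h, full sleep, and a range of true AHI values. P(exactly 4) = e^(−m) m⁴/24. At AHI 5, m = 3.75 and P = 0.194.

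| Assumed true AHI | m | P(exactly 4) | P(3 or 4) |
|---|---|---|---|
| 3 | 2.25 | 11% | 31% |
| 4 | 3.00 | 17% | 39% |
| 5 | 3.75 | 19% | 40% |
| 7.5 | 5.625 | 15% | 26% |
| 10 | 7.50 | 7% | 11% |
| 17.5 | 13.125 | 0.2% | 0.3% |
| 25 | 18.75 | about 0 | about 0 |

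Exactly 4 is the count at which dropping one event turns a segment that is not normalized into a normalized one. A count of 3 is the mirror case.

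**Step 4: what the passages establish about masking.** The angle channels share the montage, angle scoring is tied to the other data, the score sheet pairs angle with AHI, and the wedge-placing role completes scoring forms. No sentence separates knowledge of the angle from the scoring of events.

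**The case against.** The strongest reply is that the protocol is silent on masking and does not actually call for unmasked scoring. A reader might infer that respiratory events are marked with the angles on screen. The text does not say so: scoring angles in correlation with other data also fits marking events first and relating the angles afterwards. A reader might likewise infer that the technologist who places the wedges scores the night's events. Step 8 concerns forms completed once recording has begun, which may be only the Appendix A sheet, while Section 2 places the scoring after the night and names no scorer. Both limits stand. What remains is that no masking is provided and nothing rules out a scorer who knows the angle. In a single-arm study that is a feature of the design and not a detail of the analysis.

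It is also fair that the result below 5 is not the only outcome. The main aim is whether rotation affects the AHI, the secondary aim concerns percentage reduction, and Appendix A records oxygen saturation. On the AHI scale one event is 1.33/h, small beside the sheet's illustrative fall from 25 to 5. The boundary argument therefore applies to the normalization result only. The continuous AHI uses the same scored events, so it is open to the same influence, though less sharply.

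A reader might go on to compute the chance that at least one of the four rotated segments has exactly 4 events. If all four had a true AHI of 5, that is 1 − (1 − 0.194)⁴ = 58%; at 10 it is 1 − (1 − 0.073)⁴ = 26%. The protocol supports no such range for all four. Interpolating Appendix A's example values linearly gives 11.25 at 30 and 150 degrees and 20 at 60 and 120 degrees. P(exactly 4) is then 4.6% and 0.06%, and the chance of at least one is 1 − (0.954)² × (0.9994)² = about 9%. All of these also assume independent segments.

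Finally, AASM rules and the desaturation requirement limit a scorer's discretion, and Appendix A tells the user to replace its example numbers with actual values. Both points reduce the concern without removing it.

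**Conclusion.** The point holds as a gap in the design that is cheap to close. The protocol makes no provision to mask event and sleep scoring to head angle, in a study with a declared goal, example values that show lower AHI with rotation, and no control arm.

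In a segment with 45 minutes of sleep, one disputed event can change the normalization result when the count is 3 or 4. The probabilities in the table rest on Poisson counts, full sleep and assumed true AHI values. They measure how near a segment is to the threshold. They do not measure bias, and the documents allow no estimate of its size or any conclusion that bias would occur.

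**What to change.** In Section 2, at the paragraph on scoring after data collection, state that:

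1. Sleep stages and respiratory events are scored after the night with the pitch and roll channels and the wedge log hidden.
2. The event file is locked when scoring is complete.
3. The angles are then merged by time stamp and the AHI is computed per angle.
4. The investigator reviews the locked values.
5. The event count and minutes asleep are reported for each segment beside the result against 5, so that boundary cases are visible.

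Monitoring during the night and wedge placement stay as they are.

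The cost is slightly more handling per record: a display setting, a lock and a merge. No extra reader is required. Because the angle order is fixed, elapsed time can still reveal the angle, so masking is only partial unless segments are also scored in shuffled order with the clock hidden. That further step depends on the scoring software, which the protocol does not describe, and should be used where the software allows it.

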### Subject Selection:

Subject selection will be based upon the following inclusion, exclusion criteria:

#### Inclusion criteria:

- 1. Participant has provided written informed consent.
- 2. Participant is diagnosed with Positional Obstructive Sleep Apnea.
- 3. Participant age is between 21 and 60 years
- 4. If currently on PAP therapy, is able to produce compliance data within the last week before screening visit
- 5. Is able to follow directions during the overnight sleep study.
- 6. If currently on PAP therapy participant self-report that excessive daytime sleepiness persists when PAP therapy is not in use.
- 7. Able to be "off" PAP therapy for 4 nights

#### Exclusion criteria:

- 1. Documented diagnosis of Insomnia
- 2. Chronic ear infections

- 3. Persistent neck "pains".
- 4. Previous C-Spine fusion
- 5. History of Cardiac arrhythmias
- 6. History of seizures
- 7. Allergic to standard tape used in Sleep Centers
- 8. Persistent chronic posture physical issues, including shoulder issues.
- 9. Non-English speaking.
- 10. Hospitalization within the previous 4 weeks.
- 11. Use of antibiotics or steroids within the previous 4 weeks.
- 12. Any major uncontrolled disease or condition, such as congestive heart failure, malignancy, end-stage heart disease, end-stage heart disease. ALS, or sever stroke, or other condition as deemed appropriate by investigator as determined by review of medical history and/or participant reported medical history.
- 13. History of severe osteoporosis.
- 14. Excessive alcohol intake (> 6oz hard liquor, 48 oz beer or 20 oz wine daily), or illicit drug use by review of medical history and/or participant reported medical history.
- 15. Daily use of prescribed narcotics (greater than 30 mg morphine equivalent)

## Study Procedures:

- Subject (participant) how are eligible will be scheduled for a daytime screening session at the Sleep Center located at [name] with either the Study Coordinator or Staff Research Technologist. Following the screening visit and signed consent, qualified participants shall be asked to complete an overnight sleep study (polysomnogram).
- Following the screening visit, participant will be scheduled for an overnight sleep study and participant will arrive at scheduled time, generally between the hours of 7:00 PM and 8:30 PM.
- Research Technologist greets patient, verified individual personal information and matches the assigned Participant Clinical Data Binder (PCD) including the assigned study number.
- 4. Research Technologist shall complete the demographic section of the PCD and explain the sleep study to the participant.
- 5. Research Technologist shall attach electrodes as per Sleep Systems Research Montage and escort participant to assigned sleep room and will further explain to the participant the "process" of gathering sleep study data (i.e. calibrations, use of call button and the system that will be utilized to rotate the head as per protocol.)

- Research Technologist will attach forehead sensor to the most level surface of forehead without getting too close to the eyes with medical tape. Small foam wedges may be necessary under the sensor to adjust for calibration. Research Technologist will confirm the pitch and roll angles to be 90 degrees +/- 5 degrees.
- 7. Participant is allowed to watch Television or read until "Lights Out" as determined by the Research Technologist.
- 8. Once recording has commenced the Research Technologist shall complete the scoring forms as per protocol. Once the baseline AHI for POSA is verified (generally about 2 hours following sleep) Research Technologist shall enter the Sleep room and initiate neck roll maneuvers, utilizing wedge pillows as follows:
  - a) 30 degrees on right for 45 minutes.
  - b) 60 degrees on right for 45 minutes
  - c) 90 degree (head and neck aligned with supine torso) for 45 minutes
  - d) 120 degrees to left for 45 minutes
  - e) 150 degree to left for 45 minutes.

The goal is to normalize AHI (<5).

9. If no calculated AHI indicative of POSA (>5) is achieved the participant will be awakened at 7:00 AM and discharged from Sleep Center.

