## The Effect of Head Pitch and Roll Rotation Independent of Torso Position on the AHI in Positional Obstructive Sleep Apnea

## 1. Background and Study Aim

The prevalence of Obstructive Sleep Apnea (OSA) can be as high as 9% within the general population. A subset of OSA, described as Positional Obstructive Sleep Apnea (POSA), defined operationally as apneas occurring during specific positions while asleep, occurs predominantly in the supine position. Approximately 30% of obstructive sleep apnea (OSA) patients have supine-predominant OSA.(2) The patients diagnosed with obstructive sleep apnea that position dependent are at least twice as severe when sleeping supine. In one study, the prevalence of POSA was as high as 50% in patients diagnosed with mild sleep apnea (AHI, 5-15/h) and as low as 7% in patients diagnosed with severe sleep apnea (AHI > 30/hr) (1). Results from another study of 1170 adults Asian patients conducted over a span of four years, from 2004 through 2008, demonstrated that the presence of POSA is almost three-fourths of the patients and that the AHI is the most dominant factor for determining positional dependency, followed by BMI. (3)

It has been hypothesized that POSA may also occur independent of torso position but is affected solely by head position, independent of supine. A review of drug-induced endoscopy in OSA which is predominantly performed in the supine position concluded that head rotation improves upper airway collapse during this procedure in supine position. (4). Thus while the treatment of POSA has generally been directed at limiting sleeping in the supine position without regards to effects of head position, rotating the head away from the 90 degree position might alleviate the "crush force" seeking to close the upper airway. This study seeks to verify whether rotation of the head while sleeping in the supine position during polysomnography affects the calculated AHI. Head rotation will be defined in terms of degree rotation from a 90 degree starting position (head position aligned with supine position) and rotating the head from right to left defining the movement in terms of a widening angle from 0 degrees to 90 degrees through 180 degrees, thus reducing the AHI. A secondary aim is to develop an algorithm that can predict whether a specific degree of head rotation can be assigned to a percentage reduction in AHI.

The diagram below, provided by the sponsor, illustrates this maneuver:

[figure not shown]

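### One fixed order of the five head-roll settings ties each single angle's AHI to one segment of the night; reversing the order in half the participants would largely repair this

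*Protocol*

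**What the plan says.** Protocol, Study Procedures, step 8, starts the head-roll settings after the baseline: "Once the baseline AHI for POSA is verified (generally about 2 hours following sleep"). At that point the "Research Technologist shall enter the Sleep room and initiate neck roll maneuvers, utilizing wedge pillows as follows". The list runs from "30 degrees on right for 45 minutes" through 60, 90 and 120 degrees to "150 degree to left for 45 minutes". Section 2, Study Design, gives the same single direction: "the research technologist shall initiate the head roll from right to left at specific degree changes". That section also describes a non-randomized study "with the intent of enrolling up to 10 participants", with one overnight study each. No section reverses or counterbalances the order, or repeats a setting. The Appendix A score sheet holds sample values and sets no other order.

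The results have a per-angle use. The secondary aim in section 1 is an algorithm to "predict whether a specific degree of head rotation can be assigned to a percentage reduction in AHI". The data analysis section refers to predicting the roll angles that normalize the AHI, to documenting the outcome for each participant, and to possible use of the results in powering a larger trial. The Apnea Severity Calculator takes the highest AHI measured near 90 degrees as its starting value.

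**The concern.** If all participants pass through the angles in the same order, an angle effect and a time-of-night effect produce the same data. Any tendency of the AHI to rise or fall over the night is then credited to the angle used at that time. The error does not average out over participants, because all of them share the order, so a larger sample would not help. An analysis plan could not remove it either without assuming a shape for the drift. At stake are the degree-to-reduction algorithm and any effect size carried forward to a larger trial.

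**Working it through.** The plan states no sample-size or power figure that bears on this, so there is none to reproduce. The check is of the design itself.

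**Inputs (step 8 and section 2).** Baseline about 120 min; five segments of 45 min; angles 30, 60, 90, 120, 150 in that order; up to 10 participants; one night each. The drift sizes below are assumptions.

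**Timing.** Segment midpoints are 120 + 45(k − 1) + 22.5 min for k = 1 to 5, that is 142.5, 187.5, 232.5, 277.5 and 322.5 min after sleep. The correlation of angle with time is 1.00.

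**Separability.** A model with 10 participant terms, 4 angle contrasts and 4 segment contrasts has 10 + 4 + 4 = 18 parameters. In the fixed order its rank is 14, the same as participant + angle alone (10 + 4). Adding only a linear time term also leaves it at 14.

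**Size for single angles.** Let the AHI be multiplied by r per segment, with no head effect. Relative to the 90-degree segment, 30 degrees shows r^−2 and 150 degrees shows r^2:

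| r | 30 v 90 | 150 v 90 |
|---|---|---|
| 1.05 | 0.907 (−9%) | 1.103 (+10%) |
| 1.10 | 0.826 (−17%) | 1.210 (+21%) |
| 1.20 | 0.694 (−31%) | 1.440 (+44%) |

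Falling drift swaps the two sides. The 20% case is strong: 1.20^4 = 2.07, so the AHI doubles from the first segment to the last.

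**Pooled or folded angles.** With t = segment − 3, the distances from 90 are 60, 30, 0, 30, 60 at t = −2, −1, 0, 1, 2. Each distance has mean t = 0 and mean t^3 = 0, so linear, cubic and any other drift antisymmetric about the third segment cancels in complete nights. The multiplicative drift above has a small symmetric part, so pooled rotated versus 90 is (r^−2 + r^−1 + r + r^2)/4 = 1.003, 1.011 and 1.042.

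Mean t^2 is 0, 1 and 4 at distances 0, 30 and 60, so curvature does not cancel. Distance correlates 0.96 with t^2. Distance as three categories with linear time has rank 13, and adding a quadratic term leaves it at 13 of 14. As an example, an assumed AHI peak of 10%, 20% or 30% confined to the third segment gives a false pooled reduction of 1 − 1/1.1 = 9%, 1 − 1/1.2 = 17% or 1 − 1/1.3 = 23%.

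**Baseline held at 90 degrees (assumption).** The 90-degree setting is then seen at two times. Participant + angle + linear time reaches rank 15 of 15, so linear drift can be estimated. Adding a quadratic term leaves the rank at 15, so linear plus quadratic drift cannot.

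**Half listed, half reversed.** Participant + angle + segment has rank 16 of 18, and participant + angle + linear time 15 of 15. The group mean at 30 or 150 degrees relative to 90 is (r^−2 + r^2)/2, and at 60 or 120 it is (r^−1 + r)/2. At r = 1.10 the five means are 1.018, 1.005, 1, 1.005 and 1.018, against 0.826, 0.909, 1, 1.100 and 1.210 in the fixed order.

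**The case against.** The strongest reply is that the fixed order does little harm to the comparisons the protocol needs. Appendix A pairs mirror angles (45 with 135, for instance), which suggests that distance from 90 matters and not side. On that reading the order is already balanced against steady drift, and the pooled error is only 0.3% to 4.2% in the scenarios above. This stands for complete nights. It does not cover curved drift, nor an algorithm that keeps the five angles separate.

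A second reply is that linear drift can be adjusted for if the baseline is taken with the head near 90 degrees. That is correct, but step 8 does not require that head position during baseline, and curvature would remain unresolved.

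A third is that step 8 is a titration towards a normal AHI, in which order is natural. Yet it has fixed durations and no stopping rule, and it passes through neutral midway, so it works as a fixed schedule of conditions.

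Three stronger readings are tempting, and the documents do not support them. A reader might infer that a planned left-versus-right comparison is spoiled. Such a comparison would be exposed (ratio r^3, or 1.33 at r = 1.10), but no section plans one. A reader might infer that mirror-folded results are protected against linear drift alone; in fact any antisymmetric drift cancels. And a reader might infer that the AHI is known to drift by these amounts; the documents give neither size nor direction.

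**Conclusion.** The point holds in limited form. Within the five step 8 segments, single-angle AHI effects are inseparable from time of night unless a form for the drift is assumed. At an assumed 10% rise per segment, the false effect is −17% for 30 versus 90 degrees and +21% for 150 versus 90. Folded or pooled contrasts escape antisymmetric drift in complete nights but not drift with a symmetric part. Comparisons with the baseline are also ordered in time, since it always comes first.

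The consequence is a limit on how the per-angle algorithm can be read and on what can be carried into a larger trial. With no stated test and up to 10 participants, no stated result is invalidated. Severity: minor design improvement for a pilot.

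**What to change.** Keep the five settings and the 45-minute segments.

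- Once a participant's baseline AHI is verified, assign the listed order or its exact reverse, alternating from a prepared list so that half receive each. Assigning at that point means that a participant covered by step 9 ("If no calculated AHI indicative of POSA (>5) is achieved the participant will be awakened at 7:00 AM") uses up no place on the list.
- Amend the single-direction wording in section 2 to match, and record the order used.
- Include segment number in the group analysis as a linear term. As five free categories it would leave distance from 90 aliased.
- Name the 90-degree segment as the reference for percentage reduction, instead of the first-in-night baseline or a peak value.

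**Gain.** Left and right are separated, and steady drift is nearly removed from group means. Moves between settings stay at 30 degrees, and order error within a participant stays as it is now.

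**Cost.** A short amendment and an order card per participant, with no extra participants, nights or segments. Balance is approximate if unequal numbers complete the two orders. Distance from 90 stays aliased with curved time patterns (rank 16 of 18), and comparisons with baseline stay confounded with time.

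**Option, not the recommendation.** A 10-sequence Williams list would also remove the curved aliasing at group level (rank 18 of 18). It raises the mean move from 30 to 60 degrees, with moves of up to 120. At 10% drift it also widens the pooled-versus-90 error within one participant from +1% to between −21% and +28%. Since the protocol documents results for each participant, that is a real price.

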## Data Analysis, Safety, Confidentiality and Compensation:

Demographic data will be presented with descriptive analysis. Sleep Study data will be scored as per AASM (American Academy of Sleep Medicine) standards and will be tested for normal distribution with respect to prediction of neck and head roll angles normalizing the AHI (Apnea Hypopnea Index). Normalizing AHI or reducing to sufficient levels to decrease the symptoms of untreated POSA will be documented for each subject. The results of this pilot study may be used to power a larger trial.

With respect to confidentiality, a unique identification number designed to protect the identity of participant will be used to identify the participant on report forms, recruitment logs, data forms or other report containing information. Each participant will sign a HIPAA authorization

permitting the release of protected health information to the sponsor, the investigative team, and regulatory authorities.

Safety maintenance at the Sleep Center during the overnight visit shall be maintained in accordance Policies and Procedures currently in place at the Sleep Center located at [name].

Participants will be compensated for travel expenses and time commitment. Participants will be compensated \$50.00 for the screening visit and up to \$400.00 for each overnight sleep study they complete.

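### One block of at most 45 minutes of sleep per head-roll angle cannot support a yes/no reading at AHI <5 when the true rate at that angle is near 5

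*Protocol*

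**What the plan says.** Step 8 of Study Procedures lists five head-roll positions in order, beginning with "30 degrees on right for 45 minutes". Each is held once and for the same time. The step ends with "The goal is to normalize AHI (<5". Section 2 (Study Design) schedules one overnight study per participant and up to 10 participants, so no angle is repeated within a person. The Glossary divides events by total sleep time, so 45 minutes on the clock is the most that a block's denominator can be.

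The threshold is used in two further places. Section 2 has the investigator review the study "to determine whether the maneuvering of head pitch and roll had normalized the AHI (See Appendix A"). The data analysis section tests sleep data "with respect to prediction of neck and head roll angles normalizing the AHI (Apnea Hypopnea Index"). That section also documents for each subject either normalisation or a reduction large enough to ease symptoms, and gives the second option no figure. It adds: "The results of this pilot study may be used to power a larger trial". The secondary aim in section 1 is an algorithm to "predict whether a specific degree of head rotation can be assigned to a percentage reduction in AHI".

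The protocol sets no minimum sleep time per block and makes no allowance for the uncertainty of a block AHI.

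**The concern.** An AHI from a whole night rests on many events. An AHI from 45 minutes rests on a handful when the true rate is around 5/h: the expected count at exactly 5/h is 5 × 0.75 = 3.75. One scored hypopnea more or less can then decide whether an angle is called normalising.

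The error runs both ways. An angle that leaves the participant above the line may be recorded as a success, and an angle that does bring AHI below 5 may be recorded as a failure. What matters is the rate at the rotated angle, not the baseline. A manoeuvre that lowers AHI from 25 to 6 lands in the same grey zone as a mild case with no effect. The sponsor's illustrative score sheet in Appendix A shows a fall from 25 to 5, which is at the line itself.

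The stake is the study's main message, namely which angles normalise AHI and in whom, and any use of that message in planning a larger trial.

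**Working it through.** The protocol states no error rate or power, so there is no planned figure to reproduce.

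**Inputs from the protocol.** Threshold AHI <5, strict (step 8). Block length 45 min = 0.75 h, once per angle (step 8). Denominator is sleep time (Glossary).

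**Assumptions, not in the protocol.** AHI at an angle is events over sleep time in that block. Event counts are Poisson, with clustering as a sensitivity case. True AHI values are a range chosen to show where the problem lies.

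**Step 1: the cut in events (no model needed).** One event in 0.75 h moves AHI by 1/0.75 = 1.33/h. Three events give 3/0.75 = 4.0/h (pass); four give 4/0.75 = 5.33/h (fail). In general a block passes only if events < sleep minutes/12. The cut of 3 therefore holds above 36 and up to 45 min of sleep. At 36 min or less at most 2 events pass, at 24 or less at most 1, and at 12 or less only 0.

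**Step 2: what a block can show.** The exact 95% interval runs from χ²(0.025, 2n)/(2 × 0.75) to χ²(0.975, 2n+2)/(2 × 0.75).

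- 0 events: 0 to 4.9/h
- 1 event: 0.03 to 7.4/h
- 3 events (a pass): 0.8 to 11.7/h
- 4 events (a fail): 1.5 to 13.7/h

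Only a block with no events excludes 5/h from above. The intervals for the last pass and the first fail are nearly the same.

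**Step 3: chance that a block reads <5.** With h hours asleep, P(X ≤ k) for X ~ Poisson(true AHI × h), where k is the cut from step 1. For true AHI 6 and 45 min the mean is 4.5, so P = e^(−4.5) × (1 + 4.5 + 10.125 + 15.1875) = 0.342. For true AHI 8 the mean is 6, so P = e^(−6) × (1 + 6 + 18 + 36) = 0.151. The last column uses a negative binomial with variance twice the mean.

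| True AHI at the angle | 45 min asleep | 30 min asleep | 45 min, clustered |
|---|---|---|---|
| 3 | 81% | 81% | 77.5% |
| 4 | 65% | 68% | 66% |
| 5 | 48% | 54% | 54% |
| 6 | 34% | 42% | 43% |
| 8 | 15% | 24% | 25% |
| 10 | 5.9% | 12% | 14% |
| 15 | 0.4% | 2.0% | 2.5% |
| 25 | <0.01% | 0.03% | below 0.1% |

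A truly normalising angle is missed in 100 − 81 = 19% of full-sleep blocks at true AHI 3, and in 100 − 65 = 35% at true AHI 4.

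**Step 4: dependence on sleep time.** At the same true AHI of 6, the pass chance is 49% with 37 min asleep and 30% with 36 min, because the cut drops from 3 to 2 events.

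**Step 5: would a slightly longer block cure it?** Appendix A's illustrative rows are 60 min long while step 8 sets 45, and the two should be reconciled. Either way the problem remains: with 60 min asleep, true AHI 6 still passes 29% of the time and true AHI 8 passes 10%.

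**The case against.** The strongest reply is that the protocol never writes a per-angle decision rule. Step 8 gives a goal once, after the list of angles; the data analysis section documents outcomes and also allows an improvement short of normalisation. This is a small non-randomised pilot, any threshold misclassifies near the line, and a statistical analysis plan that is not shown may model AHI across angles. All of that is fair and limits the point. Still, <5 is the only criterion with a number, the analysis speaks of angles that normalise AHI, and the single block per angle is fixed in the protocol.

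A reader might infer more than the text supports:

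- *That a participant is very likely to have at least one false pass.* With no effect at any of the four rotated angles and independent blocks, the chance of at least one pass is 1 − (1 − 0.342)^4 = 81% at AHI 6 and 1 − (1 − 0.151)^4 = 48% at AHI 8. That matters only if one passing angle makes a participant normalised, and the protocol states no such rule.
- *That the verdict is read without counts or sleep time.* The visible Appendix A columns show neither, but the right edge is cropped, and section 2 has the investigator review the scored study.
- *That most baselines lie near the line.* Section 1 reports that "the prevalence of POSA was as high as 50% in patients diagnosed with mild sleep apnea (AHI, 5-15/h"), but that range is not a supine AHI, which may be higher. The illustrative baseline is 25/h. The protocol gives no share of participants near 5.
- *That manoeuvres begin as soon as AHI exceeds 5.* Step 9, "If no calculated AHI indicative of POSA (>5) is achieved", covers the case where POSA is not shown. The start is in step 8, once the baseline AHI for POSA is verified.
- *That chance normalisations will distort the next trial's power.* The protocol says the results may be used for this and does not say which quantity.

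**Conclusion.** The concern holds for angles whose true AHI is near 5, roughly 3 to 8. There, with full sleep and Poisson counts, a single block gives the wrong answer in 15% to 35% of cases at the values 3, 4, 6 and 8. Clustering raises the false passes at 6 and 8 to 43% and 25%; 30 minutes of sleep raises them to 42% and 24%. The cut in events, and its shift with sleep time, needs no model.

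It does not undermine the study's ability to see a large fall. With a true AHI of 15/h or more and full sleep, a false pass is rare (0.4%), and a drop from 25 to about 5 would be visible as a drop. What a block cannot settle is which side of 5 the result lies on. The error per block rests on assumed true rates; how many participants or angles fall in the grey zone cannot be derived from the protocol. This is an inexpensive improvement worth making, not a fatal flaw.

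**What to change.** Leave the angle schedule as it is and change what is recorded and concluded.

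1. Record the event count and the minutes of scored sleep for each angle beside its AHI, on the score sheet if they are not already there.
2. Report each per-angle AHI with an exact Poisson interval.
3. Describe the per-angle <5 reading as descriptive.
4. Base the angle conclusion on event-rate ratios against 90 degrees, pooled over participants, from a count model with log sleep time as offset, a participant effect and allowance for overdispersion. One minus the ratio is the percentage reduction that the secondary aim asks for.

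The cost is wording in the data analysis section, at most two columns on the score sheet and a little more analysis. The sleep, roll and body-position signals are already recorded, so study conduct does not change.

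There are downsides. Statements about individual participants become less definite, and with up to 10 participants the pooled ratios will be imprecise. Because step 8 runs the angles in a fixed order, the ratios remain confounded with time of night; the report should say so.
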